#### **SAMPLE SIZE JUSTIFICATION**

The sample size was determined by practical considerations and not based on statistical power calculations. Approximately four subjects will be enrolled in SAD cohort 1 (2 active treatment and 2 placebo). Approximately twelve subjects will be enrolled in each of the other SAD and MAD cohorts. They will be randomized to either active treatment (10 subjects per dose level) or placebo (2 subjects per dose level).

With ten subjects on active drug per dose group or cohort, there is a 94% chance to observe at least one AE that has an incidence rate of 25% in the population.

---

#### **INTERIM ANALYSIS**

No interim analysis is planned for this study.

---

**RO7049389—F. Hoffmann-La Roche Ltd**  
19/Protocol YP39406, Version 4

---

**LIST OF PROHIBITED MEDICATIONS**

All medications (prescription and OTC) taken within 4 weeks of study screening will be recorded on the appropriate eCRF.

As a general rule, no concomitant medication will be permitted within 14 days prior to the first dosing or within 5 half-lives of the medication prior to the first dosing (whichever is longer), until the follow-up visit, with the exception of the cases listed in the protocol. Exceptions may be made on a case-by-case basis following discussion and agreement between the Investigator and the Sponsor after the rationale for exception is discussed and clearly documented.

---

**RO7049389—F. Hoffmann-La Roche Ltd**  
20/Protocol YP39406, Version 4

## LIST OF ABBREVIATIONS AND DEFINITIONS OF TERMS

Abbreviation	Definition
AE	Adverse Events
ALT	Alanine aminotransferase
AST	Aspartate aminotransferase
AUC	Area under the curve
BID	Twice daily
BP	Blood pressure
cccDNA	Covalently closed circular DNA
CHB	Chronic Hepatitis B
CL	Clearance
CL/F	Apparent clearance
CRO	Contract research organization
CSR	Clinical study report
CTCAE	Common Terminology Criteria for Adverse Events
DDI	Drug-drug interaction
DNA	Deoxyribonucleic acid
EC	Ethics Committee
ECG	Electrocardiograms
eCRF	Electronic case report form
EDC	Electronic data capture
ESF	Eligibility screening form
FDA	Food and Drug Administration
FIH	First in human
FSH	Follicle-stimulating hormone
HBeAG	Hepatitis B envelope antigen
HBsAG	Hepatitis B surface antigen
HBV	Hepatitis B virus
HCV	Hepatitis C virus
HDL	High density lipoproteins
HIV	Human immunodeficiency virus
HR	Heart rate
IB	Investigator's Brochure
ICH	International Conference on Harmonization
IEC	Independent Ethics Committee
IFN	Interferon
IMP	Investigational medicinal product

**RO7049389—F. Hoffmann-La Roche Ltd**

21/Protocol YP39406, Version 4

IND	Investigational New Drug (application)
INR	International normalized ratio
IRB	Institutional Review Board
IUD	Intrauterine device
IV	Intravenous
LDL	Low density lipoproteins
LSLO	Last subject, last observation
LSLV	Last subject, last visit
MAD	Multiple ascending doses
NOAEL	No-observed-adverse-effect level
NUC	Nucleos(t)ide analogue
PD	Pharmacodynamic
PK	Pharmacokinetic
PT	Prothrombin time
Q12h	Twice daily, every 12 hours
Q24h	Once daily, every 24 hours
QD	Once daily
QRS	QRS complex
QT	QT interval
QTc	QT corrected for heart rate
QTcF	QT corrected for heart rate using the Fridericia correction factor
RBC	Red blood cell
RNA	Ribonucleic acid
RR	RR interval
SAD	Single ascending dose
SAE	Serious adverse event
SD	Single dose
SoA	Schedule of assessments
ULN	Upper limit of normal
V	Volume
WBC	White blood cell

**RO7049389—F. Hoffmann-La Roche Ltd**  
22/Protocol YP39406, Version 4

## **1. BACKGROUND AND RATIONALE**

RO7049389, an inhibitor of hepatitis B virus (HBV) capsid assembly, is being developed for the treatment of patients with chronic HBV infection.

### **1.1 BACKGROUND ON DISEASE**

Hepatitis B virus (HBV) infection is a major cause of both acute hepatitis and chronic liver diseases, including cirrhosis and hepatocellular carcinoma. Approximately two billion people worldwide have serological evidence of past or present HBV infection. An estimated 686,000 people are estimated to die each year due to the acute or chronic consequences of hepatitis B ([WHO 2016](#)). In China, about 7% of the population (approximately 90 million) is chronically infected with HBV ([Yu et al 2014](#); [Liang et al 2009](#)).

Chronic HBV infection can be characterized by the persistence of high levels of HBV antigens (including capsid protein, core protein, hepatitis B envelope antigen [HBeAg], and hepatitis B surface antigen [HBsAg]). Disease progression is a dynamic process with several stages, during which chronic hepatitis B may be presented either as HBeAg-positive or HBeAg-negative hepatitis.

Persistence of HBV infection is a consequence of the presence of covalently closed circular DNA (cccDNA) in the nuclei of infected hepatocytes. Despite the advancement in the understanding of HBV disease biology, eradication of cccDNA (defined as 'disease cure') may not be achievable for the foreseeable future. Nevertheless, the sustained clearance of HBsAg has been shown to be protective against disease progression and development of HBV complications including cirrhosis, liver failure and hepatocellular carcinoma (HCC). Accordingly, sustained HBsAg loss with or without seroconversion has been defined as 'functional cure', and is specified by current treatment guidelines as the ideal treatment endpoint. Achieving functional cure allows treatment cessation ([EASL 2012](#)) with low likelihood of virological relapse. Other clinically meaningful endpoints, irrespective of HBeAg status, are HBV DNA suppression and alanine aminotransferase (ALT) normalization, which indicate the virological and biochemical responses to therapies, respectively. For HBeAg-positive patients, HBeAg seroconversion is indicative of a better prognosis, including lower rates of cirrhosis and slower disease progression. For both HBeAg-positive and –negative chronic hepatitis B (CHB), sustained suppression of HBV replication is associated with biochemical remission, histological improvement and delayed disease progression. However, virological relapse is a major limitation of the currently approved therapies as they rarely result in functional cure (HBsAg loss).

Currently, there are two classes of drugs available for the treatment of CHB: subcutaneously-administered interferon (IFN) preparations, and orally-administered nucleos(t)ide analogues (NUCs). Although both types of treatment can induce the loss of HBV envelope antigen with development of anti-HBeAg antibody (serological response),

**RO7049389—F. Hoffmann-La Roche Ltd**

23/Protocol YP39406, Version 4

the suppression of HBV DNA to an undetectable level by sensitive polymerase chain reaction (PCR) methods (virological response), and are able to normalize liver transaminases levels (biochemical response), neither treatment achieves a high rate of functional cure. HBsAg loss only occurs in approximately 3% of patients after one year of treatment, and < 15% after one to five years' follow-up (EASL 2012). In addition, IFN-based therapies are associated with many side-effects, while NUCs frequently require prolonged or possibly life-long therapy, and some are associated with a high risk of viral resistance.

## 1.2 BACKGROUND ON RO7049389

RO7049389 is an inhibitor of HBV capsid assembly and belongs to the well-studied class of heteroaryldihydropyrimidine (HAP) compounds. This class of compounds induces formation of abnormal HBV core protein aggregates, which are subsequently depleted. Depleting functional core protein results in interruption of viral assembly and inhibition of HBV replication.

The HBV core protein is involved in multiple steps of the viral life cycle such as encapsidation of pre-genomic ribonucleic acid (pgRNA), and subsequent initiation of reverse transcription. It is also an important component of the cccDNA mini chromosome. Furthermore, it has been suggested that the HBV core protein may play a role in suppressing host innate immune responses (Twu et al 1998; Fernandez et al 2003; Gruffaz et al 2013). Depletion of functional core protein may therefore facilitate host immune restoration. RO7049389 can therefore potentially provide anti-HBV benefits by both direct inhibition of viral replication and augmentation of host immune responses against the virus.

See the [RO7049389 Investigator's Brochure](#) for more details on non-clinical and clinical studies.

### 1.2.1 Previous Non-Clinical Studies

RO7049389 has shown potent antiviral activity through the induction of HBV core protein misassembly and subsequent degradation, and has a high degree of selectivity against HBV. RO7049389 demonstrated activity against most prevalent HBV genotypes (A, B, C, D) and against a panel of nucleos(t)ide analogue-resistant HBV variants tested in vitro.

RO7049389—F. Hoffmann-La Roche Ltd  
24/Protocol YP39406, Version 4

The image consists of five horizontal rows, each containing a series of black bars of varying widths. Between these black bars are white spaces. In the center of each white space, there is a small, dark, vertical mark. This mark is approximately one-third the width of a black bar and has a slightly irregular, bracket-like shape. The entire pattern is repeated five times across the width of the image. The background is a solid white color.

RO7049389—F. Hoffmann-La Roche Ltd  
25/Protocol YP39406, Version 4

A high-contrast, black and white image showing a dark, irregular shape on a white background. The dark shape has several white, stepped or jagged edges, particularly along the top and right sides. The overall appearance is abstract and geometric.

## RO7049389 had no effect on neurobehavioral and respiratory function in rats

An in vitro study indicated that RO7049389 had no phototoxic potential.

See the [RO7049389 Investigator's Brochure](#) for further details on non-clinical studies.

### 1.2.2 Previous Clinical Studies

The first-in-human (FIH) study with RO7049389 is ongoing. YP39364, a randomized, Sponsor-open, Investigator-blinded, subject-blinded, placebo-controlled study to investigate the safety, tolerability, pharmacokinetics and pharmacodynamics of RO7049389 in: (1) single- (with or without food) and multiple (with microdosing midazolam) ascending doses in healthy volunteers; (2) patients chronically infected with hepatitis B virus.

As of the data cutoff of 2 June 2017, preliminary PK analysis was performed using data from 59 healthy volunteers treated across five SAD cohorts ( $n=33$ ) and three multiple ascending-dose (MAD) cohorts ( $n=26$ ). Subjects in the SAD cohorts received a single dose of RO7049389 (150–2000 mg) or placebo; those in the MAD cohorts were treated with twice-daily RO7049389 (200 or 400 mg) or placebo for 14 days. [REDACTED]

RO7049389—F. Hoffmann-La Roche Ltd  
26/Protocol YP39406 Version 4

[REDACTED]

[REDACTED]

Preliminary blinded safety review was performed in Study YP39364 for 59 healthy volunteers. Thirty-three subjects in five SAD cohorts (150, 450, 1000, 2000, and 1000 mg repeated cohort) received a single dose of RO7049389 or placebo, and 26 subjects in three MAD cohorts (200 mg fasted, 200 mg fed, 400 mg fed) received RO7049389 or placebo BID for 14 days. This preliminary safety review showed that both the single doses and BID dosing were well tolerated in all subjects.

[REDACTED]

See the [RO7049389 Investigator's Brochure](#) for further details on clinical studies.

### **1.3 STUDY RATIONALE AND BENEFIT–RISK ASSESSMENT**

#### **1.3.1 Study Rationale**

Study YP39406 is designed to assess the safety, tolerability and pharmacokinetics (PK) of single-ascending (SAD) and multiple-ascending doses (MAD) of RO7049389 in healthy Chinese subjects. The study leverages data generated in the FIH study YP39364, allowing targeted evaluation of fewer doses. The data generated from this study will help to evaluate potential ethnic differences between Chinese and non-Chinese subjects with regards to safety, tolerability and pharmacokinetic characteristics

**RO7049389—F. Hoffmann-La Roche Ltd**  
27/Protocol YP39406, Version 4

that will provide guidance on future clinical studies and optimize the benefit-risk in Chinese HBV patients.

### **1.3.2 Benefit/ Risk Assessment**

As this is a Phase I study in healthy subjects, no therapeutic benefit is anticipated for these subjects. However, this study will be essential in the development of new treatments for chronic HBV infection in populations of Asian descent, and for selecting the most appropriate dose for a proof-of-concept study in such patients.

The evaluation of the potential risks of treatment and the specific tests, observations, and precautions required for clinical studies with RO7049389 are based on information from non-clinical toxicology and safety pharmacology studies. Furthermore, this study leverages data generated in the ongoing FIH study YP39364. Safety and tolerability will be carefully assessed, and study subjects will be closely monitored. Section 6 of the [Investigator's Brochure](#) (Guidance to the Investigator) summarizes key risk management activities to consider when dosing this novel compound.

Based on (i) the calculation of a safe starting-dose for the first-in-human study as recommended in the Food and Drug Administration (FDA) guidance ([FDA 2005](#)), and on (ii) exposure multiple calculations, the selected starting-dose of 200 mg is considered to be safe (please refer to Section [3.1.2](#) for details). The target exposure range of RO7049389 proposed within this study has been shown to be safe and well-tolerated in pre-clinical studies, and under a controlled setting, should provide a better understanding of clinical safety and tolerability to guide future clinical studies. All dose-levels to be included in this study will be within the dose-range which will have been considered to be safe and well-tolerated in the FIH study YP39364. The risks for an individual study subject due to ascending doses of RO7049389 or study-related procedures are considered to be minimal. The starting-dose level of 200 mg may be adjusted based on the available data from FIH study YP39364.

## **2. OBJECTIVES**

### **2.1 PRIMARY OBJECTIVE**

The primary objective of this study is as follows:

- To assess the safety and tolerability of RO7049389 compared to placebo after single- and multiple-ascending oral doses in healthy Chinese subjects.

### **2.2 SECONDARY OBJECTIVE**

The secondary objective of this study is:

- To assess the pharmacokinetics (PK) of RO7049389 after single-ascending and multiple-ascending oral doses in healthy Chinese subjects.
- To investigate metabolites (M5, M6, and M11) of RO7049389 in selected plasma samples.

**RO7049389—F. Hoffmann-La Roche Ltd**

28/Protocol YP39406, Version 4

### 3. STUDY DESIGN

#### 3.1 DESCRIPTION OF STUDY

[figure not shown]
##### 3.1.1 Overview of Study Design

This study will leverage the data which will have been generated in the FIH study, allowing targeted evaluation of fewer doses.

Healthy subjects will be enrolled into one of 3 planned cohorts and one optional cohort. Cohort 1 will include 4 healthy subjects, with 2 randomly assigned to RO7049389 and 2 assigned to placebo. From Cohort 2 to Cohort 4, each of the cohorts will include 12 healthy subjects with 10 subjects randomly assigned to RO7049389 and 2 subjects randomly assigned to placebo.

In Cohort 1, subjects will receive one single dose of the assigned study medication. In subsequent cohorts, subjects will receive one single dose of the assigned study medication, followed by a wash-out period of approximately 1-week before entering into a MAD phase of the study. Subjects in the MAD cohorts will be from the SAD cohorts after the wash-out period (see [Figure 1](#)), or from new enrollments if there are discontinuations between the SAD phase and MAD phase for reasons other than safety.

**Figure 1 Overall Study Design and Dose-escalation**

Dotted lines indicate optional cohorts. See [Table 1](#) for additional information.

Escalation to the next single dose cohort will be based primarily on the safety and available PK data through 24 hours post-single dose in the previous cohorts. The MAD phase may start after a wash-out period of approximately 1-week, providing that the safety information through 24 hours post-dose in the SAD phase at the same cohort, and available safety information in the entry-into-human study (YP39364), have been reviewed.

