## **STUDY DESIGN**

### **Description of Study**

Healthy subjects will be enrolled into one of 3 planned cohorts and one optional cohort. Cohort 1 will include 4 healthy subjects, with 2 randomly assigned to RO7049389 (200mg) and 2 assigned to placebo. From Cohort 2 to Cohort 4, each of the cohorts will include 12 healthy subjects with 10 subjects randomly assigned to RO7049389 and 2 subjects randomly assigned to placebo.

In Cohort 1, subjects will receive one single dose of the assigned study medication. In subsequent cohorts, subjects will receive one single dose of the assigned study medication, followed by a wash out period of approximately 1-week before entering into a MAD phase of the study. Subjects in the MAD cohorts will be from the SAD cohorts after the wash out period, or from new enrollments if there are discontinuations between the SAD phase and MAD phase for reasons other than safety.

Escalation to the next single dose cohort will be based primarily on the safety and available PK data through 24 hours post single dose in the previous cohorts. The MAD phase may start after a wash out period of approximately 1-week, providing that the safety information through 24 hours post dose in the SAD phase at the same dose level, and available safety information from MAD cohorts in the entry-into-human study (YP39364), have been reviewed.

---

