### **3.1.2 Dose-Escalation Decision Criteria**

A Safety Review of the data will be conducted by the Principal Investigator, the Medical Monitor, and the Sponsor Clinical Team prior to each RO7049389 dose-escalation.

Escalation to the next dose cohort will be based primarily on the safety and tolerability information (including adverse events [AEs], electrocardiograms [ECGs], vital signs, clinical laboratory test results) up to 48 hours post-dose (SAD), and secondarily on all available PK data up to 24 hours post-dose (SAD) in a minimum of 8 subjects (receiving active study drug or placebo) within the previous cohort. Doses will be escalated by three-fold increments but for higher doses the increments will be smaller than three-fold. The decision to escalate the dose will be made by mutual agreement between the Sponsor and the Investigator.

The MAD phase (Cohorts 2, 3, and 4) can begin after a washout period of at least one week, and once safety and tolerability information through 24 hours post-dose in the SAD phase (see [Figure 1](#)), and available safety and tolerability information from MAD cohorts in the entry-into-human study (YP39364) have been reviewed. Additionally, both the Sponsor and the Investigator must agree that the safety data can support continuing with the multiple-dose phase.

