#### **3.1.2.1 Dose-Escalation Stopping Rules**

Any serious adverse event considered related to study drug will lead to an immediate halt of study drug dosing, dose escalation and enrollment of new subjects until a thorough investigation has been conducted by the Sponsor's Clinical Team and the Principal Investigator. The sponsor or designee will notify all investigators and IRBs/EC, if required (see Section [5.3](#)), regarding the outcome of such investigation. The study will only continue if agreed by the IRBs/EC.

An internal safety review of the unblinded data by Sponsor representatives from Translational Medicine, Drug Safety, Clinical Pharmacology and Biostatistics will be performed prior to each RO7049389 dose-escalation.

Planned dose-escalation will not be implemented if one of the following circumstances occurs in subjects treated with RO7049389, unless it is obvious that the occurrence is not related to the administration of study medication:

- If at any dose level, more than two subjects on active drug experience:
  - Severe and clinically significant (as defined by the Investigator) RO7049389-related AEs of the same character.

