**RO7049389—F. Hoffmann-La Roche Ltd**

31/Protocol YP39406, Version 4

- Clinically significant RO7049389-related laboratory abnormalities of the same character (e.g., ALT or AST $>3\times$ ULN, and total bilirubin $>2\times$ ULN).
- Clinically significant RO7049389-related changes in vital signs or ECGs of the same character (e.g., QTcF $>500$  msec, or  $>60$  msec longer than the pre-dose baseline, within the first 48 hours post-dose).
- It is predicted that further dose-escalation will not result in a further increase in plasma exposure.

- The proposed dose *or exposure* exceeds those previously evaluated in the study YP39364.
- Other findings (regardless of the incidence rates) that at the joint discretion of the Sponsor and the Investigator indicate dose-escalation should be halted.

If dose-escalation is stopped, lower doses within the tolerated dose range could be investigated, or a dose repeated in the subsequent cohorts by mutual agreement between the Sponsor and Investigator, in order to increase the amount of data within this tolerated dose range.

For an individual subject, dosing should not continue if there are:

- Clinically significant RO7049389-related changes in safety parameters that are considered not acceptable by the Investigator and/or the Sponsor; or
- Poor gastrointestinal (GI) tolerability that is considered to affect the subject's wellbeing and/or the PK evaluation.

Due to the exploratory nature of this clinical study, its conduct can be discontinued at any time at the discretion of the Sponsor. This will not constitute a premature termination of the study.

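### The safety window for escalating the single dose is 24 hours in the synopsis and Section 3.1.1 but 48 hours in Section 3.1.2

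*Combined protocol and SAP*

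**What the plan says.** Three places in the current Version 4 text describe the data needed before the next single-dose cohort is opened.

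- Synopsis, Description of Study: escalation is "based primarily on the safety and available PK data through 24 hours post single dose in the previous cohorts".
- Section 3.1.1, in the paragraph after Figure 1: the same sentence, "based primarily on the safety and available PK data through 24 hours post-single dose in the previous cohorts".
- Section 3.1.2, Dose-Escalation Decision Criteria: escalation rests primarily on safety and tolerability information "up to 48 hours post-dose (SAD), and secondarily on all available PK data up to 24 hours post-dose (SAD".

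Starting the MAD phase is a separate decision with its own sentence. Section 3.1.2 allows it "once safety and tolerability information through 24 hours post-dose in the SAD phase" has been reviewed, and Section 3.1.1 likewise asks for "the safety information through 24 hours post-dose in the SAD phase at the same cohort".

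Section 3.1.2.1 then lists what blocks a planned escalation. One group of criteria is count-based: "If at any dose level, more than two subjects on active drug experience" related events or changes of the same character. Its ECG example is a QTcF above 500 msec, or more than 60 msec "longer than the pre-dose baseline, within the first 48 hours post-dose". A later bullet in the same list lets the Sponsor and Investigator jointly halt escalation for any other finding, however few subjects show it.

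**The concern.** The window fixes the minimum safety follow-up that must exist before more healthy volunteers receive a higher dose. As written, a team that follows the synopsis or the overview could treat 24 hours of safety data as enough. Under Section 3.1.2 the same act would be a deviation. No clause says which section prevails.

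The stopping rules point the same way as Section 3.1.2. Their QTcF example looks at the first 48 hours, so a decision taken at 24 hours would be taken before that example could be fully observed. The safety reviews held before each escalation do not settle the matter, because the window defines what data those reviews must have in front of them.

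**Working it through.** The plan attaches no calculated figure to this point, so the check is a comparison of texts and some simple counting.

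**1. The texts side by side**

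| Decision | Place | Safety window | PK window |
|---|---|---|---|
| Next SAD cohort | Synopsis | 24 h | 24 h |
| Next SAD cohort | Section 3.1.1 | 24 h | 24 h |
| Next SAD cohort | Section 3.1.2 | 48 h | 24 h |
| Start of MAD phase | Synopsis, 3.1.1 and 3.1.2 | 24 h | not stated |

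The conflict is confined to the safety window for SAD escalation. The MAD-start window is the same in all three places. None of this relies on the summary of changes.

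**2. Could the 24 hours apply to PK only?** The sentence in the synopsis and Section 3.1.1 puts safety and PK under one time limit, so 24 hours for both is the natural reading. If it is read as PK only, those two places state no safety window at all.

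**3. Size of the difference.** 48 − 24 = 24 hours per escalation. Table 1 has four SAD levels (200, 400, 600 and 800 mg), which gives 4 − 1 = 3 escalations. Without optional Cohort 4 there are 3 − 1 = 2.

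**4. Which escalations can 24–48 hour data affect?**
- Count-based criteria: more than two means at least 3 active subjects at a dose level. Section 3.1.1 states that "Cohort 1 will include 4 healthy subjects, with 2 randomly assigned to RO7049389 and 2 assigned to placebo". Since 2 < 3, these criteria cannot be met in Cohort 1. Cohorts 2 to 4 have 10 active subjects each, so they can be met there. They can therefore bear on 3 − 1 = 2 escalations (400 to 600 mg and 600 to 800 mg), or on 2 − 1 = 1 without Cohort 4.
- Other-findings clause: it has no minimum count. A marked QTcF change in one Cohort 1 subject could stop the step from 200 to 400 mg. Data from 24 to 48 hours can therefore matter at all 3 escalations, or at both if Cohort 4 is not run.

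**5. Dose context.** Section 1.2.2 reports first-in-human single doses from 150 to 2000 mg, described as well tolerated in a preliminary blinded review. 800 / 2000 = 0.40.

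**6. Time cost of 48 hours.** Relative to the 24-hour text, 3 × 24 h = 72 h = 3 days in total, or 2 × 24 h = 48 h = 2 days without Cohort 4. Dosing is on the morning of Day 1 (Section 4.3.2.1), so 48 hours falls on the morning of Day 3, the planned discharge day (Section 3.1.1.1).

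**7. Is Section 3.1.2 sound enough to copy from?** Only in part. Its sentence also requires data from at least 8 subjects in the previous cohort, and Cohort 1 has 4. Since 4 < 8, that requirement cannot be met for the step from 200 to 400 mg.

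**The case against.** The strongest reply is that the texts can be obeyed together. The synopsis and overview say what escalation mainly rests on. They do not cap the data or say that escalation may happen at 24 hours. A team that waits 48 hours satisfies all three places on timing, while one that escalates at 24 hours breaches Section 3.1.2, which is headed as the decision criteria and is the more detailed text. This stands. A reader might infer that the protocol is impossible to follow, or that it plainly authorises escalation at 24 hours, and the documents support neither. What remains is that the natural reading of two prominent places sets a shorter safety basis than the criteria section.

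A second reply is that little is at stake. The doses are to stay within the range considered safe in the first-in-human study, subjects remain in clinic to Day 3 under either text, and both a joint safety review and an unblinded Sponsor review precede each escalation. This also stands. A reader might infer a material hazard to subjects, but nothing in the documents supports that.

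A third reply is that Section 3.1.2 may itself be the stale text, given its 8-subject minimum. That is fair as a caution. It could change which text should be corrected, but the conflict would still be there. The 48-hour QTcF example and the clinic stay to Day 3 both fit 48 hours as the intended window.

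Finally, a reader might infer from the 2 active subjects in Cohort 1 that late QTcF data cannot affect the first escalation. That is true only of the count-based criteria. The other-findings clause applies in every cohort.

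**Conclusion.** The inconsistency is real and should be corrected, although the practical risk is small. It amounts to 24 hours of required safety follow-up at each of 3 SAD escalations, or 2 without Cohort 4, and data from those hours can matter at every one of them. These counts describe the stated rule and are not an estimate of risk.

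The conclusion rests on the joint 24-hour reading of the sentence in the synopsis and Section 3.1.1, and on the projected dose levels in Table 1, which the protocol allows to be adjusted. How many ECGs, laboratory tests or other assessments fall between 24 and 48 hours is set in Appendices 1–4. Those are not in the supplied text, so the amount of data affected cannot be established here.

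**What to change.** In the synopsis and in Section 3.1.1, reword the SAD escalation sentence so that it refers to *safety and tolerability data through 48 hours and available PK data through 24 hours post-dose*. Leave the 24-hour safety window for starting the MAD phase as it is.

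This borrows only the time window from Section 3.1.2 and changes no dose level, dose step or other criterion. The 8-subject minimum in that section needs its own correction for the 4-subject Cohort 1.

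The cost is a wording change in two places. Compared with the 24-hour text it adds at most about one day per SAD escalation. A team already following Section 3.1.2 loses no time, and no clinic stay is added.
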